1.3 Dimensions of respectful maternity care

In this study, the revised typology of RMC by Bohren *et al.* based on a systematic review of 65 studies from 34 countries would be used. Bohren *et al.* recently build on earlier work of Bowser and Hill⁶ and revised the dimensions of RMC to include seven domains: physical abuse, sexual abuse, verbal abuse, stigma and discrimination, failure to meet professional standards of care, poor rapport between women and health providers, and health system conditions and constraints described in table 1.^{7,14}

Table 1. Typology of respectful maternity care during institutional delivery

Third-Order Themes	Second-Order Themes	First-Order Themes
Physical abuse	Use of force Physical restraint	 Being beaten, pushed, pinched, slapped or poked to facilitate the delivery Physically restrained, tied or gagged during labour and delivery
Sexual abuse	Sexual abuse	- Sexual abuse or rape
Verbal abuse	Harsh language Threats and blaming	 Harsh or rude language Judgmental or accusatory comments Threats of withholding treatment or poor outcomes Blaming for poor outcomes
Stigma and discrimination	Discrimination based on sociodemographic characteristics Discrimination based on medical conditions	 Discrimination based on ethnicity/race/religion Discrimination based on HIV status Discrimination based on age Discrimination based on socioeconomic status
Failure to meet professional standards of care	Lack of informed consent and confidentiality Physical examinations and procedures Neglect and abandonment	 Lack of informed consent process Breaches of confidentiality Painful vaginal exams Refusal to provide pain relief Performance of unconsented surgical operations Neglect, abandonment, or long delays Skilled attendant absent at time of delivery
Poor rapport between women and providers	Ineffective communication Lack of supportive care Loss of autonomy	 Poor communication Dismissal of women's concerns Language and interpretation issues Poor staff attitudes Lack of supportive care from health workers Denial or lack of birth companions Women treated as passive participants during childbirth Denial of food, fluids, or mobility Lack of respect for women's preferred birth positions Denial of safe traditional practices Objectification of women Detainment in facilities
Health system conditions and constraints	Lack of resources Lack of policies Facility culture	 Physical condition of facilities Staffing constraints Staffing shortages Supply constraints Lack of privacy Lack of redress Bribery and extortion Unclear fee structures Unreasonable requests of women by health workers

The dimensions presented in table 1 are based on Bohren revised typology of RM C^{14}

2 Aims

This study aims to (i) generate empirical evidence on the quality of maternal and newborn health care as it relates to the frequency and nature of respectful maternity care during institutional delivery in

Gombe state, (ii) to improve measurement methods for respectful maternity care and (iii) to inform state-level and global actions to better promote respectful maternity care.

3 Objectives

- *Obj 1* To determine the prevalence of RMC during institutional delivery in Gombe state.
- *Obj 2* To validate self-report of respectful maternity care.
- Obj 3 To determine the utilities associated with different dimensions of RMC in Gombe state.
- Obj 4 To provide feedback to government and grantees promoting RMC in Gombe state.
- *Obj 5* To engage other groups promoting RMC both within and outside Nigeria.

4 Study design and methods

4.1 Study setting

This study will build on ongoing IDEAS project's research activities in Gombe state. The study will be conducted in the same settings as the IDEAS ongoing surveys including household clusters and health facilities.

Briefly, Gombe State is one of the 36 states of the Federal Republic of Nigeria, located in the North-East region of the country. Gombe State has an estimated population of 2.8 million, based on 2011 projections from the 2006 national census, and an annual population growth rate of 3.2%. Gombe State is multi-ethnic and comprises 11 Local Government Areas (LGA). About 75% of the state is rural, with farming, cattle herding and trading as the predominant occupations. Gombe State has a high fertility rate of 7.0 live births per 1,000 females aged 15-49 and a high maternal mortality ratio.^{2,15}

Four grantees are implementing innovations aimed at generating demand for MNH services, promoting lifesaving interventions at home, improving the quality of health services, accountability and responsiveness of the health system in 57 wards and 57 priority health facilities out of a total of 114 wards in Gombe state — IDEAS project defines these 57 wards as 'intervention area' and the remaining 57 wards being 'comparison area'.

4.2 Study implementation

The study will be conducted in three phases 1) formative, 2) data collection and 3) data analysis, synthesis and dissemination phases:

Formative phase – a formative research will be carried out to identify an appropriate tool, generate additional items, adapt and translate the tool into Hausa language. The first phase will involve a comprehensive review of the literature to be followed by informal consultation and review of the identified tool (and its items) with women and local experts in Gombe to ensure appropriateness, and

pilot testing (alongside the IDEAS surveys) and refining the adapted tool. Data source in formative phase will come from published and grey literature on RMC in LMIC and pilot data from household surveys, observation of birth, exit interview and birth attendant interview. Data collection and analysis will be performed between November of 2016 and May 2017.

Data collection phase — will involve (a) generating data on prevalence of RMC during facility-based childbirth from household surveys (June July 2017, May-July 2018), observation of birth and exit interviews (June July 2017, November December 2017) — the prevalence of RMC will be assessed in subsequent IDEAS household surveys, observation of births, birth attendant interviews and exit interviews to update indicators of RMC in the results framework; (b) in-depth interviews and focus group discussions (FDG), the qualitative studies will seek to explore women experience from their recent facility-based birth (i.e. women-health worker interaction & condition of place of delivery) in Gombe, identify the attributes and attribute levels and generate items for the choice experiment: 3) conduct the choice experiments at follow-up (at home) 6-months later in November December 2017.

Analysis and synthesis phase — will involve continuous sharing of findings with the grantees and government and engagement with groups working on RMC both within and outside Nigeria and wider dissemination of result findings — to catalyse changes and inform future policy and practice towards promoting RMC in Gombe, Nigeria and globally. All data collection instruments and procedures will be thoroughly pilot-tested prior to being used. Data collection instruments will be embedded within the IDEAS surveys except for the in-depth interviews and focus group discussion. Table 2 shows the different phases of implementation of the study and how each data collection activity contributes to the study objectives.

Table 2. Phases of implementation

	2016			2017			2018			2019				Contributing to:			
	Q	Q	Q	Q	Q	Q	Q	Q	Q	Q	Q	Q	Q	Q	Q	Q	
	1	2	3	4	1	2	3	4	1	2	3	4	1	2	3	4	
Literature review																	Obj 1+2+3
In-depth interviews																	Obj 3
FDGs																	Obj 3
Household survey																	Obj 1+4+5
Observation of births																	Obj 2+4+5
Exit interviews																	Obj 2+4+5
Home follow-up																	Obj 3+4+5
DCE																	Obj 3+4+5
Dissemination																	All

5 Sampling, data collection methods and sources

This section describes the data collection method, data sources and sampling strategy, arranged in order of study objective.

5.1 Household survey

Sample — prevalence of respectful maternity care at the population level (objective 1) will be determined through household survey data. IDEAS project conducts an annual household survey each year 2017-2018. The annual household survey use cluster sampling with 40 intervention household clusters and 40 comparison household clusters from 'priority' and 'non-priority' areas respectively, to generate population level coverage estimate of MNH indicators from women aged 13-49 years with livebirth 24 months prior to each survey. Each household cluster is defined as an enumeration area segmented to include 75 households. Enumeration areas are selected using simple random sampling from a list of all enumeration areas in each area. 3000 households are sampled in each area, a total of 6000 from the 80 clusters (40 intervention and 40 comparison clusters). From this sample, approximately 2000 women with recent birth are expected in total from the 6000 households, minimum of 100 women in each area (each 40 clusters). At each household, the household head is interviewed about residents and socio-economic characteristics, and each resident woman aged 13-49 is individually interviewed. Interviewed women with a live birth in the 12 months prior to survey are asked to complete a detailed survey module about their experiences during pregnancy through to post-partum periods for that birth.

Sample size - The previous household survey indicated coverage of institutional delivery to be 46%, thus the expected number of interviews with women who delivered in a facility in the last two years is approximately 1000. To estimate a proportion of 0.5 (most conservative) with high precision (to within +/- five percentage points) and with 95% confidence the required number of interviews with women who delivered in a facility is 593 (after adjusting for a cluster effect of 1.4 and 10% losses). The prevalence of an illustrative set of RMC indicators is shown in table 3. These indicators suggest that the conservative sample size estimate is appropriate across the range of indicators, while allowing the potential for further analysis as the project proceeds (for example to compare proportions over time, or to restrict births to those that occurred in the last 12 months rather than 2 years).

Table 3: Prevalence of illustrative RMC indicators based on observations of birth in 10 primary health facilities, March 2017

Indicator	Levels from 'clinical observation of birth' March 2017
% of women with a recent birth allowed birth companion during labour and delivery	58
% of women with a recent birth with desired physical privacy during labour and delivery	23
% of women with a recent birth listened to and provided support during labour and delivery	55
% of women with a recent birth informed of what will happen during labour and delivery	47
% of women attended to by skilled birth attendant	32

The next section describes IDEAS health facility survey, the second quantitative data source for the study, and which component of the health facility survey contributes to the study objectives.

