Protocol for a study to investigate the prevalence and nature of respectful maternity care during institution delivery in Gombe State, Nigeria and to improve measurement methods for respectful care

Investigators

[name] (Research Fellow, ITD, DCD/ IDEAS Project Country Coordinator, Nigeria) [name] (Associate Professor, ITD, DCD)

IDEAS Project
Informed Decisions for Actions to Improve Maternal and Newborn Health
London School of Hygiene & Tropical Medicine

Abbreviations and acronyms

ANC Antenatal Care

BMGF Bill and Melinda Gates Foundation

HFW Health Facility Workers

LGA Local Government Authority

MNCH Maternal Newborn and Child Health

MDGs Millennium Development Goals

PHC Primary Health Care

RMC Respectful Maternal Care

SDGs Sustainable Development Goals

SAQIP Social Accountability and Quality Improvement Project

SPHCDA State Primary Health Care Development Agency

SBA Skilled Birth Attendant

WHO World Health Organization

1 Background

Reducing the deaths of women during pregnancy, childbirth or within forty-two days of termination of pregnancy from causes related to the pregnancy or its management remains a global priority, and a major challenge to the Nigerian health systems.^{1,2} Pregnancy related outcomes nationally are far from the acceptable levels enshrined in the past Millennium Development Goals (MDGs) and the current Sustainable Development Goals (SDGs). Worst still, are maternal mortality and morbidity indices in the Northeastern Nigerian states consisting of Adamawa, Bauchi, Gombe, Maiduguri, Taraba and Yobe states, which remained alarmingly poor in comparison to other Nigerian states.²

To address this challenge, substantial investments have been made and multiple strategies have been implemented in the past, driven by national institutions or international organisations, aimed at improving institutional deliveries with skilled assistance, an evidence based lifesaving intervention, though they have had limited success.³ Increases in the proportion of women delivering at health facilities have been marginal in Nigeria. In more than a decade, institutional delivery only increased by a 3-percentage point: 33% (in NHDS 2003), 35% (in NDHS 2008) and 36% (in NDHS 2013).^{2,4} In a recent household survey in Gombe state, more than 60% of women delivered at home in 2016.¹

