1.2 Overview of this study

The IDEAS project is part of this wide partnership with GSPHCDA, Pact, SFH, C4C and E4A working on MNH in Gombe, as a measurement, learning and evaluation (MLE) grant. IDEAS project aims to improve the health and survival of mothers and babies through generating evidence to inform policy and practice. In line with IDEAS project's overarching aim, the study described here will generate empirical evidence on the quality of MNH care as it relates to the frequency and nature of RMC during institutional delivery in Gombe state, to inform state-level and global actions to better promote RMC, and to improve measurement methods for RMC. The study will aim to answer the following the research questions:

Q 1 What is the prevalence of respectful maternity care during institutional delivery in Gombe State? (Objective 1)

To be determined in two ways: 1) prevalence of respectful maternity care based on how frequently mothers regarded the interaction with health workers or health facility conditions

during their last institutional delivery to be respectful, through household surveys of mothers with births in the 24 months prior to interview; 2) prevalence of RMC based on how frequently the interactions with health workers or facility conditions during institutional delivery are deem (by general consensus) to be humiliating or undignified, through observation of births (in line with submission by Freedman et al¹¹).

Q 2 What is the validity of self-reported measures of respectful maternity care?

To be determined by comparing observable respectful maternity care behaviors documented during observation of births as gold standard measures of RMC, compared to reported occurrence of RMC during exit interview with observed women on discharge from facility and again during household-follow interview with observed women 6-12 months after birth to test the validity of self-reporting i.e. do women report their experience of RMC consistently, and extent of normalization of RMC i.e. the extent to which some aspect of RMC are normalized in Gombe.

Q 3 What utilities do women attach to dimensions of respectful maternity care during institutional delivery in Gombe State?

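### Protocol section 5.1 counts facility births over 24 months but gives the care-experience module only to women with a birth in the last 12; if the module window governs, the required 593 and the ±5 points are probably missed.

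*Protocol*

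**What the plan says.** Research question 1 (Protocol section 1.2) measures prevalence "through household surveys of mothers with births in the 24 months prior to interview". Section 5.1 defines the survey population with the same 24-month window.

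The sample-size paragraph of section 5.1 sets the aim: "To estimate a proportion of 0.5 (most conservative) with high precision (to within +/- five percentage points) and with 95% confidence". The required number of facility-birth interviews is "593 (after adjusting for a cluster effect of 1.4 and 10% losses"). Against this, with 46% facility delivery among about 2000 women with a recent birth, "the expected number of interviews with women who delivered in a facility in the last two years is approximately 1000".

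The sentence in section 5.1 on who is asked about care uses a different window: "Interviewed women with a live birth in the 12 months prior to survey are asked to complete a detailed survey module". That module covers experiences from pregnancy to the post-partum period for that birth. The paragraph on sample size later mentions restricting to births in the last 12 months as one possible further analysis.

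Two other inputs do not fit. The Background says that "more than 60% of women delivered at home in 2016", and section 5.1 gives a "minimum of 100 women in each area (each 40 clusters").

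**The concern.** Objective 1 is a descriptive precision objective, so its sample size rests on how many women with a facility birth answer the respectful-care questions. The count that clears 593 covers two years of births. The only module described as covering the birth goes to women with a birth in one year. Section 4.2 says that the study's instruments are embedded in the IDEAS surveys, so the IDEAS module is the natural place for these items.

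The look-back is an eligibility filter in a questionnaire programmed on tablets (section 6.2). If it is set at 12 months, second-year births yield no Objective 1 data, and no later analysis plan can recover them. It therefore has to be settled in the protocol.

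**Working it through.** **Inputs, all from section 5.1:** proportion 0.5, half-width 0.05, 95% confidence, design effect 1.4, losses 10%, 2000 women with a recent birth, 46% facility delivery, about 1000 facility births expected.

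**1. The plan's own figure.** n0 = 1.96² × 0.25 / 0.05² = 384.2 (384.1 with an unrounded quantile), rounded up to 385. Then 385 × 1.4 = 539 completed interviews, and 539 × 1.10 = 592.9, so 593. The stated figure reproduces.

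**2. Expected facility births over 24 months.** 2000 × 0.46 = 920, stated as about 1000. Both exceed 593.

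**3. Expected facility births over 12 months.** The protocol does not give the share of these births that falls in the last 12 months. With an even split (assumed), 920 / 2 = 460 and 1000 / 2 = 500. Against 593 the shortfall is 133/593 = 22% or 93/593 = 16%.

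**4. Half-width** = 1.96 × √(1.4 × 0.25 / n), in percentage points:

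| Births asked | n before losses | Half-width | n after 10% losses | Half-width |
|---|---|---|---|---|
| 24 months, stated count | 1000 | 3.7 | 900 | 3.9 |
| 24 months, 2000 × 46% | 920 | 3.8 | 828 | 4.0 |
| 12 months, half of 1000 | 500 | 5.2 | 450 | 5.5 |
| 12 months, half of 920 | 460 | 5.4 | 414 | 5.7 |

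Both loss treatments are shown because the protocol calls the expected count a number of interviews and does not say whether losses are already out.

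**5. Sensitivity to the even split.** Reaching 593 needs a 12-month share of 593/1000 = 59% to 593/920 = 64%. If the expected counts are already net of losses, the bar is 539 and the share needed is 54% to 59%. At a 55% share the counts are 506 to 550 (5.2 to 4.9 points before losses, 5.4 to 5.2 after). At 60% they are 552 to 600 (4.9 to 4.7 before, 5.2 to 5.0 after).

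The share of women can exceed one half because a woman with a birth in each year counts once, by her later birth. With equal numbers of births in the two years and a fraction o of last-year mothers who also gave birth the year before, the share is 1/(2 − o). A share of 0.593 needs o = 0.31, and 0.645 needs o = 0.45. That is a large fraction, so a modest departure from an even split does not rescue 593.

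**6. Other proportions.** For the Table 3 indicators at n = 460 before losses, the half-width is 5.3 to 5.4 points for levels of 47 to 58%, 5.0 at 32% and 4.6 at 23%. After losses (n = 414) it is 5.6 to 5.7, 5.3 and 4.8.

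**The case against.** The strongest reply is that the protocol nowhere says the respectful-care items sit only in the 12-month module. Every resident woman aged 13 to 49 is interviewed individually, and the items could be placed there. Research question 1, the survey population and the sample-size count all say 24 months. Listing a 12-month restriction as a possible further analysis makes sense only if 24-month data exist. On that reading the precision target is met comfortably. This stands, and it makes the shortfall conditional. It does not remove the contradiction: the sentence on further analysis presupposes data that the module sentence, read literally, does not collect.

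The loss of precision is also modest, and no test or decision rule in the protocol hangs on the margin. That stands too.

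Three stronger readings are tempting and are not supported:

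- **That the survey will miss ±5 points.** This treats an inference about where the items sit, and an assumed even split, as facts.
- **That only 400 or fewer facility births are expected** (2000 × 0.40 / 2). This puts the Background's home-delivery figure in place of the 46% in the sample-size paragraph. The two should be reconciled, but section 5.1 does not date or define the survey behind its 46%, so the lower rate cannot simply be substituted.
- **That precision could collapse to what 100 women per area would give.** The same sentence expects about 2000 women from two equal areas, or 2000 / 2 = 1000 each. The 100 is probably a typing error, and at most a floor rather than an expected yield.

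**Conclusion.** Section 5.1 contradicts itself, and contradicts research question 1, on which births supply the Objective 1 data. If the items are asked only in the 12-month module and births are spread evenly, about 460 to 500 facility births are expected against 593. The half-width at a proportion of 0.5 is then 0.2 to 0.4 points wider than the stated 5.0 before losses, and 0.5 to 0.7 wider after. If all 24-month facility births are asked, it is about 3.7 to 4.0 points and there is no precision problem. The contradiction is certain; the shortfall depends on those two assumptions.

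The difference between 920 and about 1000 is rounding and changes nothing under the 24-month reading. Nor would a 40% facility rate: 2000 × 0.40 = 800, still above 593.

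Fieldwork is planned for "household surveys (June July 2017, May-July 2018"), so 24-month windows from the two rounds overlap. That concerns comparison over time, which section 5.1 lists only as potential further analysis. It is a separate, secondary matter.

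**What to change.** Settle the look-back before the tablet questionnaire is fixed, in one of two ways:

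- **(a)** State that the respectful-care items go to every woman with a facility birth in the prior 24 months, in line with research question 1 and the sample-size count, and give the expected number as about 920. The cost is some added interview time with women who are already being visited.
- **(b)** Keep the 12-month window, change research question 1 and the sample-size paragraph to match, and restate the expected number as about 460 to 500 and the precision as about ±5.2 to 5.7 points, with the assumed 12-month share given. The cost is wording and a less favourable stated precision.

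Either way, say whether the expected number is before or after losses. Reconcile the 46% facility-delivery rate with the Background's home-delivery figure, and derive the expected count from one rate. Check the per-area minimum of 100 against the roughly 1000 per area that the same sentence implies.
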